7. DATA HANDLING

7.1. Sources of Data Used in Analyses

The data used for analysis will come from 4 main sources: the Interactive Web/Voice Response System (IXRS), the e-CRF, the clinical events committee (CEC) database, and the Clinical Trial Management System (CTMS) database. Data from the IXRS will be used to determine trial assignment (ISCHEMIA or ISCHEMIA-CKD) and treatment group. The e-CRF will be the source for site-level geographic information, all baseline and follow-up data, and will also contain data entered by the central core labs (CCTA, ECG, angiography, imaging). The CEC will provide adjudicated endpoints for primary analyses and auxiliary data, such as highest marker values associated with MI events, for secondary analyses. The CTMS database will provide site-level dates of site activation and deactivation. Primary analyses of outcomes by treatment will pool data from across all sites and will not stratify by site.

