5. RANDOMIZATION METHODOLOGY

Enrollment and randomization is accomplished by contact with the interactive web/voice randomization system (IXRS). When a participant meeting site-determined clinical and stress imaging criteria has provided informed consent, the study coordinator or investigator at the site will call or log into the IXRS to receive a participant identification number. At this point the participant is registered as enrolled. In order to randomize the participant, the study coordinator or investigator must call or log into the IXRS a second time. Participants meeting all clinical and site inclusion criteria are then randomized to either the INV or CON strategy and registered as randomized. Ischemia severity is determined by sites and is reported according to independent core laboratory review. Randomization information, including the randomized treatment assignment, is transmitted to the participant's electronic case book within the electronic data capture (EDC) system.

The original randomization scheme for ISCHEMIA was a permuted block design with stratification by enrolling site to balance the distribution of treatment assignments within the sites. The block sizes for each site were chosen at random to reduce the likelihood of an investigator predicting the next treatment group assignment. Beginning in March 2014, ISCHEMIA's randomization system was modified to facilitate enrollment of participants into the ISCHEMIA-CKD ancillary trial. The randomization lists that were originally generated for ISCHEMIA were subsequently used for randomizing both ISCHEMIA and ISCHEMIA-CKD participants together. Assigned participant identification numbers are different depending on whether the participant was enrolled in ISCHEMIA-CKD or the ISCHEMIA main trial. Details about distinguishing between ISCHEMIA-CKD and ISCHEMIA main trial participants can be found in the SAP Appendix for Definitions and Reporting Conventions.

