9.2. Demographics and clinical history

Baseline demographic and clinical characteristics will be tabulated by region and treatment group for the ITT population. The occurrence of incidental findings of clinical significance on study-related CCTA will be summarized overall and by type (ascending aortic dissection, descending aortic dissection, aortic aneurysm, large pleural effusion, pulmonary embolism, pulmonary mass, non-calcified pulmonary nodules \geq 4mm, pulmonary infiltrate, pneumothorax, and moderate or large pericardial effusion).

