In addition to Cox regression, cumulative endpoint event rates will be estimated as a function of follow-up time in each treatment group using Kalbfleisch & Prentice's nonparametric estimator of the cumulative incidence function (CIF) [6]. The Kalbfleisch & Prentice CIF estimator is equivalent to the Kaplan-Meier[7] estimator when applied to endpoints that are not subject to competing risks. It was selected for this study in order to account for the competing risk of non-cardiac deaths in the analysis of the primary endpoint and the occurrence of any type of death in the analysis of individual non-fatal endpoints. Cumulative endpoint event rates and differences in cumulative endpoint event rates for INV versus CON at yearly time points will be estimated and presented with 95% confidence intervals. These non-parametric analyses are important for descriptive purposes, to assess overall clinical impact, and will be a focus of interpretation if the event rate curves cross [8, 9]. These non-parametric analyses may also be used to construct summary measures of treatment effect which are interpretable when the proportional hazards assumption is violated. [9, 10]

In addition to comparing overall outcomes for the two randomized groups, we will perform additional analyses to assess whether the treatment effect varies according to pre-specified participant baseline characteristics, as described in Section 10.6 below.

Finally, as a sensitivity analysis, the analyses described in this section will be repeated in the Protocol Version 2.0 population and the core-lab ischemia population, as defined in Section 6.2 and 6.3 above.

10.4.1. Cox model for primary endpoint analysis.

As noted above, analysis of the primary endpoint will be adjusted for covariates and will be performed using the framework of Cox regression. Pre-specified covariates will consist of the following:

- Age
- Sex
- Estimated glomerular filtration rate (eGFR)
- Ejection fraction
- Diabetes

Covariates were selected on the basis of their established prognostic importance in other SIHD cohorts, highly complete data capture, and a sufficient range of values for risk to vary among participants meeting trial eligibility criteria. The following definitions and data handling conventions will be adopted:

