10.6.1. Covariates for HTE analyses

Pre-specified baseline covariates (primary interest)

- Core-lab determination of moderate or severe ischemia on stress test
- Diabetes
- New onset or worsening angina within 3 months
- Participants who have a high level of medical therapy optimization at baseline, defined as participants with all of the following characteristics at baseline:
 - Systolic blood pressure < 140 mmHg (a secondary analysis will be completed incorporating a systolic blood pressure goal of < 130 mmHg)
 - LDL <70 mg/dL and on any statin
 - Not smoking
 - Taking aspirin

Another pre-specified baseline covariate of primary interest is the severity and extent of CAD as determined by core lab review of pre-randomization CCTA for those who have had that procedure completed.

Other pre-specified baseline covariates of interest

- Ejection fraction
- Estimated GFR

Ejection fraction and estimated GFR were not included in the list of pre-specified baseline covariates of primary interest due to the fact that it was anticipated that these covariates would have insufficient variation to be able to detect an appreciable difference in the treatment hazard ratios across the range of the covariates.

The following other baseline covariates are expected to be analyzed for descriptive purposes and completeness: age, sex, imaging modality (nuclear, echo, CMR, non-imaging ETT), prior MI, prior PCI, prior CABG, prior catheterization (≤ 12 months, > 12 months, none), severity of angina as assessed by the SAQ and Canadian Cardiovascular Society (CCS) Class.

Another pre-specified baseline covariate of interest is the presence of anterior ischemia for those participants with adequate stress imaging from the baseline screening process. **As discussed in Section 10.5, analysis of participants with core-lab determination of moderate or severe ischemia is of particular scientific interest and will constitute a major pre-planned secondary analysis.**

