11. INTERIM ANALYSES

The primary objective of interim analyses is to ensure the safety of the participants enrolled in the trial and to evaluate the accumulating endpoint data by treatment group to test for possible differences favoring either of the two randomized management strategies. In addition, interim monitoring will involve a review of participant recruitment, compliance with the study protocol, status of data collection, an assessment of whether control group event rates are consistent with the rates hypothesized in the sample size calculations, and other factors which reflect the overall progress and integrity of the study including potential geographic differences. Details of the study's major planned interim analyses are documented below.

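### Is it a flaw that randomization is blocked by site, while the outcome analyses pool all sites and none is planned by site or region?

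*SAP*

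**What the plan says.** SAP Section 5 describes the scheme as a "permuted block design with stratification by enrolling site", with block sizes chosen at random. From March 2014 the same lists were "subsequently used for randomizing both ISCHEMIA and ISCHEMIA-CKD participants together".

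Section 7.1 then states: "Primary analyses of outcomes by treatment will pool data from across all sites and will not stratify by site". No reason is attached. The Cox model of Sections 10.4 and 10.4.1 adjusts for age, sex, eGFR, ejection fraction and diabetes, and Section 10.8 uses the same set for the secondary clinical endpoints. The sensitivity analyses change the population and not the model: "as a sensitivity analysis, the analyses described in this section will be repeated in the Protocol Version 2.0 population and the core-lab ischemia population".

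Section 10.6.1 lists the covariates for heterogeneity of treatment effect. Its broadest list begins "The following other baseline covariates are expected to be analyzed for descriptive purposes and completeness: age, sex, imaging modality". Site, country and region appear in none of the lists.

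Geography does appear elsewhere. Section 8 groups 39 countries into 7 regions for the enrollment summary. Section 9.2 says "Baseline demographic and clinical characteristics will be tabulated by region and treatment group for the ITT population". Section 11 places under interim monitoring "other factors which reflect the overall progress and integrity of the study including potential geographic differences".

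**The concern.** A common rule is that the analysis should reflect the factors used to restrict randomization. Here site is the only such factor and it is left out without explanation. If baseline risk varies between sites, a model that ignores site can misstate the standard error and lose some power.

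There is also a question of reporting. The trial spans 39 countries, tabulates baseline data by region and watches geography during the trial, yet the main SAP text plans no final clinical outcome by region. A regional result produced after unblinding would be post hoc. At stake would be the calibration of the primary test and a reader's ability to judge whether the result holds across settings.

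**Working it through.** **1. The plan's own figures.** SAP Section 4 gives 5,179 participants, 80% power for an 18.5% relative reduction in the 4-year rate, and a margin of error of 1.17.

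- SE of the log hazard ratio = ln(1.17)/1.96 = 0.0801.
- Events at 1:1 allocation = 4/0.0801² ≈ 623.
- For a 4-year conservative-arm rate p, HR = ln(1 − 0.815p)/ln(1 − p). The updated p is not stated. At p = 0.18, HR = 0.799.
- Power = Φ(|ln HR|·√623/2 − 1.96) = 79.8% at p = 0.18, 78.1% at 0.14 and 80.7% at 0.20.

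The stated 80% reproduces, and site is not an input to it.

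**2. Validity.** Within a site, allocation is random and nearly balanced. The lists shared with the CKD trial loosen exact balance among main-trial participants. They do not bias it, because the participant number that separates the two trials is issued at enrollment, before randomization. Omitting a prognostic stratum that was balanced by design tends to overstate the standard error, which makes the test conservative. If the SE were overstated by 2%, the correct margin would be exp(0.98 × ln 1.17) = 1.166 instead of 1.170.

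**3. Pooled against site-stratified and region-stratified log-rank tests.** The documents give neither site numbers nor between-site variation, so both are assumed: 100 to 400 sites and an SD of the site log-hazard of 0 to 0.6. The simulation used N = 5,179, blocks of 2 or 4 within site, and HR 0.797 under the alternative. It ran 1,500 null trials and 1,000 alternative trials per row, so the Monte Carlo SE is about 0.6 points for type I error and 1.2 for power.

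| Sites | SD | Type I, pooled | Type I, by site | Power, pooled | Power, by site | Power, by region |
|---|---|---|---|---|---|---|
| 100 | 0 | 4.7% | 4.5% | 83.5% | 83.1% | 83.4% |
| 100 | 0.3 | 4.8% | 4.9% | 80.7% | 80.7% | 81.0% |
| 100 | 0.6 | 4.5% | 5.1% | 77.9% | 80.1% | 78.7% |
| 200 | 0.3 | 4.7% | 5.0% | 79.4% | 78.7% | 79.3% |
| 200 | 0.6 | 4.1% | 4.5% | 76.9% | 77.1% | 77.4% |
| 400 | 0 | 4.8% | 5.1% | 83.4% | 80.7% | 83.5% |
| 400 | 0.3 | 4.8% | 5.2% | 82.1% | 79.8% | 82.1% |
| 400 | 0.6 | 3.7% | 5.2% | 78.3% | 79.0% | 78.9% |

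The pooled test never exceeds 5%. Stratifying by site changes power by −2.7 to +2.2 points and costs most when sites are many and small.

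**4. Pooled against region strata and a shared site frailty.** A second simulation used 6,000 trials per setting and 150, 320 or 500 sites, with assumed log-hazard SDs of 0.3 (site) and 0.2 (region). About 11% of list slots were removed to mimic CKD participants. Exponential models stood in for Cox, without the five covariates.

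- Pooled type I error: 5.37%, 4.73% and 4.52%. The Monte Carlo SE is √(0.05 × 0.95/6000) = 0.28 points, so all three lie within 2 SE of 5%.
- Power change under HR 0.80 (paired SE): region strata +0.10 (0.14), −0.02 (0.13), +0.20 (0.12); frailty +0.25 (0.15), +0.33 (0.13), +0.37 (0.11) points.
- Margin under the null: 1.167 for all three models.
- Pooled and frailty models reached different verdicts in 0.7% to 1.3% of trials.
- With strong variation (SDs 0.5 and 0.4, 320 sites): pooled type I error 4.25%, power gains 0.65 (region) and 1.43 (frailty) points, different verdicts in 2.6%.

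**5. What a regional breakdown could show.** A region with 10% of the events has about 62, so its margin is exp(1.96 × 2/√62) = 1.65. Two equal halves of 312 events each could detect, with 80% power, only a ratio of hazard ratios of exp(2.80 × √(8/312)) = 1.57.

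**The case for a change.** The best case for the concern comes from the SAP itself. The primary MI definition in Section 10.1 uses troponin limits reported by each site. Section 10.5 records that, from October 2014, most sites no longer needed a core-lab reading of ischemia before randomization. Section 10.12 promises to look for consistency across subgroups. Section 10.6 explains why the primary heterogeneity list is short, but that does not explain leaving region off the longer descriptive list.

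Most of this is answered elsewhere in the plan. Section 10.3 repeats the MI analyses with the secondary definition, which uses the manufacturer's 99th percentile where it is known. Section 10.4 repeats the primary analysis in the core-lab ischemia population. These address the two site-dependent elements more directly than a site term would, since a frailty or stratified model lets baseline risk vary but assumes one treatment effect. A frailty hazard ratio is also conditional on site, so a gap between it and the pooled hazard ratio is not a clean check. Region strata do not condition on site, which is the factor actually used in randomization.

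What stands is narrow: no reason for pooling is written down, and region is absent from the listed covariates. Whether geography is taken up elsewhere cannot be settled, because the SAP appendices, the separate SAP for angina and quality of life, and the full protocol were not available for this review.

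**Conclusion.** The concern does not hold. Pooling is stated openly in advance, is valid under site-blocked randomization, and does not inflate type I error. With moderate between-site variation, the region-stratified and frailty alternatives move power by less than 0.4 points and leave the margin unchanged. With strong variation the gain reaches about 1.4 points for a frailty model and about 2 points for full site stratification, and the cost of ignoring site is a slightly conservative test.

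These sizes rest on assumed site numbers, variances, block sizes and follow-up, and on simplified models. The direction follows from the randomization scheme and does not depend on those values. The absence of a regional outcome table is a reporting preference about an estimate that would be imprecise, and it leaves the primary test and its conclusion untouched.

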7.2. Methods for Handling Missing Data

Every effort will be made to obtain complete data. In the unlikely event that there is missing data, rules on how to handle the missing data will be used. These rules for how to handle the missing data will be discussed in appropriate places in the analysis plan below. Further details on how missing data will be handled can be found in the SAP Appendix for Definitions and Reporting Conventions.

In general, all available data will be included in data listings and tabulations. Population denominators will be displayed in column headers. Individual denominators will be displayed for each summary such that the amount of missing values will be evident. Participants who withdraw from the study or are lost to follow-up will still be included in the denominators for any proportions where data are available prior to study withdrawal or when the participant is lost to follow up.

8. ENROLLMENT SUMMARY

An enrollment summary will be provided by geographic region and country. Country information will be obtained from the clinical database. Countries will be grouped as follows:

Regions	Countries
North America	Canada, USA
Europe	Austria, Belgium, France, Germany, Hungary, Italy, Lithuania, Macedonia, Netherlands, Poland, Portugal, Romania, Serbia, Spain, Sweden, Switzerland, United Kingdom.
Latin America	Argentina, Brazil, Mexico, Peru
Asia	China, India, Japan, Korea, Malaysia, Russia, Singapore, Taiwan, Thailand
Pacifica	Australia, New Zealand
Africa	Egypt, South Africa
Middle East	Israel, Saudi Arabia, United Arab Emirates

The total number of enrolled and randomized participants and enrolling sites will be tabulated by region, country and overall for review by the DSMB and study leadership.

9. BASELINE SUMMARIES

9.1. Definition and timing of baseline variables

For most summaries, the baseline value is the value given closest to the date and time of randomization. Weight, heart rate, and blood pressure are measured per protocol at the time of randomization or up to 30 days prior. Baseline laboratory assessments (lipids, HbA1c, liver enzymes, complete blood counts, chemistry panel) are based on the most recent lab results available within 6 months prior to the randomization or up to 2 weeks post randomization if pre-randomization laboratory results are unavailable. Age will be computed as the difference in years between the participant's date of birth and

randomization date. Body Mass Index (BMI) will be computed as weight (kg) / ((height (cm)/100)²). Obesity will be defined as values of BMI 30 kg/m² or higher.

9.2. Demographics and clinical history

Baseline demographic and clinical characteristics will be tabulated by region and treatment group for the ITT population. The occurrence of incidental findings of clinical significance on study-related CCTA will be summarized overall and by type (ascending aortic dissection, descending aortic dissection, aortic aneurysm, large pleural effusion, pulmonary embolism, pulmonary mass, non-calcified pulmonary nodules \geq 4mm, pulmonary infiltrate, pneumothorax, and moderate or large pericardial effusion).

9.3. Protocol-assigned catheterization in the INV group

Core-lab angiographic findings from the first post-randomization diagnostic catheterization procedure in participants assigned to INV will be summarized by the frequency distribution of the number of native vessels with at least 50% stenosis and the percentage of participants with at least 50% stenosis in specific locations (left anterior descending [LAD] disease, proximal LAD disease, circumflex disease, right coronary artery disease, left main disease). Summaries of native vessel stenosis will be presented for all participants and for the subset with no prior CABG. For participants with prior CABG, summaries will include the number vein or arterial grafts with \geq 70% stenosis and the number of arterial grafts with at least \geq 70% stenosis. Other scores summarizing the extent and/or severity of disease may be reported in supplemental analyses and reports.

10. ANALYSIS OF CLINICAL ENDPOINTS

10.1. CEC adjudication

CEC-adjudicated endpoints include CV death, myocardial infarction, resuscitated cardiac arrest, hospitalization for unstable angina, hospitalization for heart failure, and stroke. Definitions of these endpoints are included in the CEC Charter.

Two versions of MI will be adjudicated in ISCHEMIA: a Primary Definition and Secondary Definition. Each definition includes a hierarchy of markers and threshold values as well as a set of rules for diagnosing MI when one or more key elements of the medical record are missing. The Primary Definition is based upon the Universal Definition of MI (UMI) [1] for Types 1, 2, and 3 MIs, but relies upon site-reported MI decision limits for troponin (which may or may not be the same as the manufacturer 99% upper reference limit (URL)). In contrast, for MI after PCI or CABG (Type 4a, 5), CK-MB is the preferred biomarker and takes precedence over troponin, and unlike the UMI, troponin is compared against the site-reported MI Decision Limit. The Secondary Definition is based closely on the UMI definition, but includes contingencies to allow diagnosing MI when various elements of the medical record are missing. Troponin is compared against the 99% URL from the assay manufacturer's package insert if known and against the laboratory-specific MI Decision Limit if the manufacturer 99th percentile is unknown. Additional supporting criteria (e.g. angiographic and ECG) are identical to the UMI definition for Type 4a MI. Analysis plans below refer to the Primary Definition unless otherwise specified.

Confirmed MI events will also be classified by the CEC as “complicated” or “not complicated” using criteria outlined in the CEC charter. The intent of the “complicated” designation is to identify a subset of MIs with features highly associated with poor prognosis. A complicated MI includes MIs occurring with serious complications such as hemodynamic instability, cardiogenic shock, a drop in ejection fraction greater than 10%, life-threatening ventricular arrhythmias, or acute heart failure.

For all confirmed MI events, the CEC will record highest marker values for Troponin I, Troponin T, CK, and CKMB when these markers are available. The laboratory-specific upper limit of normal (ULN) will be recorded for all types of markers and the manufacturer-specified upper reference limit (i.e. the 99th percentile; URL) will be recorded for Troponins only.

Confirmed MIs will be classified by the CEC using MI types provided by the UMI as follows:

- Type 1: Spontaneous MI
- Type 2: Secondary MI
- Type 3: Sudden Death MI
- Type 4a: MI related to PCI
- Type 4b: MI related to stent thrombosis
- Type 4c: MI related to stent restenosis
- Type 5: MI related to CABG

There will be some secondary analyses that will group together several MI types. There will be two resulting groups of MI types that will be analyzed. One group will correspond to procedural MIs and include Type 4a and 5 MIs. The other group will correspond to non-procedural MIs and include Type 1, 2, 4b and 4c MIs.

